8.4. Prior and Concomitant Medication

Prior medication will be defined as medication that ends prior to dosing. Concomitant medication will be defined as medication that starts during or after dosing or starts but does not end prior to dosing.

Prior and concomitant medications will be coded using the World Health Organization Drug Dictionary (WHODrug) Global, Format B3, Version March 2021 (or later if a new version is issued during the study; see the data management plan [DMP] for more details). Prior and concomitant medications will be listed.

8.5. Pharmacokinetic Assessments

8.5.1. Pharmacokinetic Analysis

The following PK parameters will be determined where possible from the plasma concentrations of CBP-307 and moxifloxacin using noncompartmental methods in validated software program Phoenix WinNonlin (Certara, Version 8.1 or higher):

Moxifloxacin (Days 1 and 16)

Parameter	Units ^a	Definition
C_{max}	ng/mL	maximum observed concentration
t_{max}	h	time of the maximum observed concentration
$AUC_{0-t_{last}}$	h*ng/mL	area under the concentration-time curve from time 0 to the time of the last quantifiable concentration (t_{last}) ^b
AUC_{0-24}	h	area under the concentration-time curve over the time interval from 0 to 24 hours post dose

CBP-307 (Days 1, 6 and 15)

AUC _{inf}	h*ng/mL	area under the concentration-time curve from time 0 extrapolated to infinity ^c (Day 15 only)
AUC _{0-t_{last}}	h*ng/mL	area under the concentration-time curve from time 0 to the time of the last quantifiable concentration (t _{last}) ^b
%AUC _{extrap}	%	percentage of area under the concentration-time curve due to extrapolation from the last quantifiable concentration to infinity (Day 15 only)
AUC ₀₋₂₄	h	area under the concentration-time curve over the time interval from 0 to 24 hours post dose
C _{max}	ng/mL	maximum observed concentration
t _{max}	h	time of the maximum observed concentration
t _{last}	h	time of the last quantifiable concentration
t _{1/2}	h	apparent terminal elimination half-life (Day 15 only)
CL/F	L/h	apparent total clearance (Day 15 only)
V _z /F	L	apparent volume of distribution during the terminal phase (Day 15 only)

^a Units are based on concentration units (provided by the bioanalytical lab or preferred units for presentation of PK parameters) and dose units used in the study.

^b The AUC will be calculated using the linear trapezoidal rule for increasing concentrations and the logarithmic rule for decreasing concentrations (linear up/log down rule).

^c Based on the last observed quantifiable concentration

Additional PK parameters may be determined where appropriate.

Pharmacokinetic analysis will be carried out where possible using actual dose administered (mg) and actual postdose blood sampling times. If an actual time is missing, the sample concentration result will be treated as missing unless there is scientific justification to include the result using the nominal time.

The parameters C_{max}, t_{last}, and t_{max} will be obtained directly from the concentration-time profiles. If C_{max} occurs at more than 1 timepoint, t_{max} will be assigned to the first occurrence of C_{max}.

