4. STUDY DESIGN

This will be a Phase I, randomized, double-blind, double-dummy, placebo-controlled, positive-controlled, multi-site, 3-arm study to investigate the effects of therapeutic and supratherapeutic oral doses of CBP-307 on the QTc interval in healthy male and female subjects.

Potential subjects will be asked to read and sign an informed consent form (ICF). After informed consent is obtained, screening procedures and tests to establish subject eligibility to enter the study will be performed within 28 days before Day 1. After informed consent has been obtained but prior to the initiation of study treatment administration, only SAEs will be reported. After placebo administration to all subjects on Day -1, all AEs, whether volunteered, elicited, or noted upon physical examination, will be recorded throughout the study (ie, from Day -1 until the end of the study).

In this study, approximately 68 healthy subjects (at least 30% for each sex) will be randomized into 2 groups (Group 1 and 2) with 34 subjects in each. Group 2 consists of 2 sub-groups (Group 2A and 2B) and each sub-group will be randomized with 17 subjects. Randomized subjects will receive the assigned study drug as a single dose in the morning on Days 1, 2, 3 to 6, 7 to 15, and on Day 16 (placebo will be administered to all subjects on Day -1).

The following treatments will be administered:

- Starting doses of CBP-307 for titration (0.05 mg on Day 1 followed by an up-titrated dose of 0.1 mg on Day 2)
- A therapeutic dose of CBP-307 (0.2 mg, Days 3 to 6)
- A supratherapeutic dose of CBP-307 (0.5 mg, Days 7 to 15)
- Placebo (matched to moxifloxacin and CBP-307)
- Moxifloxacin (400 mg)

Moxifloxacin will be used as a positive control to determine the assay sensitivity of this study with an expected peak QT effect (placebo-corrected change-from-baseline QTcF; $\Delta\Delta QTcF$) of 10 to 15 msec.

[figure not shown]
A summary of dosing timelines per Group is shown below:

Study Treatment Name	Treatment Group	CBP-307	CBP-307 Matched Placebo	Moxifloxacin (Avelox)	Moxifloxacin Matched Placebo
Dosage Formulation		Capsule	Capsule	Tablet	Tablet
Unit Dose Strength(s)/Level(s)		0.05 mg 0.1 mg	Not applicable	400 mg	Not applicable
Dosage Frequency					
Day -1	Group 1 Group 2A Group 2B		1 capsule 1 capsule 1 capsule		
Day 1	Group 1 Group 2A Group 2B	1 × 0.05 mg		1 × 400 mg	1 tablet 1 tablet
Day 2	Group 1 Group 2A Group 2B	1 × 0.1 mg			
Days 3 to 6	Group 1 Group 2A Group 2B	2 × 0.1 mg			

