8.5.1.1. Criteria for the Calculation of Apparent Terminal Elimination Rate Constant and Half-life

The start of the terminal elimination phase for each subject will be defined by visual inspection and generally will be the first point at which there is no systematic deviation from the log-linear decline in concentrations.

The apparent terminal elimination rate constant (λ_z) will only be calculated when a reliable estimate can be obtained using at least 3 data points, preferably not including C_{max}, and the adjusted coefficient for determination of exponential fit (R²-adj) of the regression line is ≥ 0.7 . Parameters requiring λ_z for their calculation (eg, AUC_{inf}, t_{1/2}, CL/F, and V_z/F for Profile Day 15) will only be calculated if the R²-adj value of the regression line is ≥ 0.7 .

The following regression-related diagnostic PK parameters will be determined, when possible:

Parameter	Units	Definition
λ_z	1/h	apparent terminal elimination rate constant
λ_z Upper	h	end of exponential fit
λ_z Lower	h	start of exponential fit
λ_z N	NA	number of data points included in the log-linear regression
λ_z Span Ratio	NA	time period over which λ_z was determined as a ratio of $t_{1/2}$
R ² -adj	NA	adjusted coefficient for determination of exponential fit

Where possible, the span of time used in the determination of λ_z (ie, the difference between λ_z Upper and λ_z Lower) should be ≥ 2 half-lives. If the λ_z Span Ratio is < 2 , the robustness of the $t_{1/2}$ values will be discussed in the clinical study report (CSR).

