8.5.1.2. Criteria for Calculation and Reporting of Area Under the Concentration-time Curve

The minimum requirement for the calculation of AUC will be the inclusion of at least 3 consecutive concentrations above the lower limit of quantification. If there are only 3 consecutive concentrations, at least 1 should follow C_{max} .

If the extrapolated area is $>20\%$, AUC_{inf} (and derived parameters) may be excluded from the summary statistics at the discretion of the sponsor or pharmacokineticist.

8.5.1.3. Criteria for Handling Concentration Below the Limit of Quantification or Missing Concentrations for Pharmacokinetic Analys

Plasma concentrations below the limit of quantification (BLQ) will be assigned a value of 0 before the first measurable concentration and thereafter BLQ concentrations will be treated as missing. The following rules apply to the specific situations defined below:

- If an entire concentration-time profile is BLQ, it will be excluded from PK analysis.
- Where 2 or more consecutive concentrations are BLQ at the end of a profile, the profile will be deemed to have terminated and any further quantifiable concentrations will be set to missing for the calculation of the PK parameters, unless they are considered to be a true characteristic of the profile of the drug.
- If a predose plasma concentration is missing, it will be set to 0 by default within Phoenix WinNonlin for the first dosing day (Study Profile Day 1).
- For multiple dose part of the study (Study Profile Day 15), if the CBP-307 concentration at 24 hours postdose is missing, this may be substituted with the predose.

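### The SAP makes Day 15 CL/F depend on λz, which implies Dose/AUCinf on a multiple-dose profile; the formula should be stated and based on AUC0-24

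*SAP*

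**What the plan says.** The CBP-307 parameter table in SAP section 8.5.1 lists CL/F as "apparent total clearance (Day 15 only" and Vz/F as "apparent volume of distribution during the terminal phase (Day 15 only". Neither row has a formula. The same table gives AUCinf for Day 15 only, as "area under the concentration-time curve from time 0 extrapolated to infinity", and AUC0-24 for Days 1, 6 and 15, as "area under the concentration-time curve over the time interval from 0 to 24 hours post dose". The section says PK calculations use the dose actually given.

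Section 8.5.1.1 groups AUCinf, t1/2, CL/F and Vz/F as examples of parameters that cannot be obtained without λz. It makes them conditional on the quality of the terminal fit: "CL/F, and V_z/F for Profile Day 15) will only be calculated if the R²-adj value of the regression line is ≥ 0.7".

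Section 8.5.1.2 adds: "If the extrapolated area is $>20\%$, AUC_{inf} (and derived parameters) may be excluded from the summary statistics", at the discretion of the sponsor or pharmacokineticist.

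On the dosing history, section 4 has 0.05 mg on Day 1, 0.1 mg on Day 2, 0.2 mg on Days 3 to 6, and then "A supratherapeutic dose of CBP-307 (0.5 mg, Days 7 to 15", once each morning. Section 8.5.1.3 itself describes the Day 15 profile as belonging to the multiple-dose part of the study. No steady-state clearance is defined, and nothing links CL/F to AUC0-24.

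**The concern.** In noncompartmental analysis CL/F needs λz only when its denominator is AUCinf. Dose/AUC0-24 needs no terminal slope. Placing CL/F among the λz-dependent parameters therefore points to Dose/AUCinf, which is the single-dose formula.

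On Day 15 that formula divides one 0.5 mg dose by an area that includes drug left from fourteen earlier daily doses. The result is too low by the accumulation factor, and Vz/F inherits the error through its AUC term. The factor depends on each subject's half-life, so the between-subject spread would be distorted as well as the mean. Clearance and volume would then be reported as properties of the drug when they partly reflect the dosing history.

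**Working it through.** **Plan's own figure.** The SAP states no half-life, clearance or accumulation ratio for CBP-307, so there is nothing to reproduce. The results below are shown over an assumed range of half-lives.

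**Inputs from the SAP.** Doses as in section 4 (0.05, 0.1, 4 × 0.2 and 9 × 0.5 mg); dosing interval 24 h; CBP-307 samples out to 96 h after the Day 15 dose (section 4); linear-up/log-down AUC rule (section 8.5.1).

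**Closed form.** Let k = ln 2 / t1/2. For a mono-exponential decline from C0 after the Day 15 dose:

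- AUCinf = C0 / k
- AUC0-24 = C0 × (1 − e^(−24k)) / k
- AUCinf / AUC0-24 = R = 1 / (1 − e^(−24k))

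At steady state AUC0-24 = Dose/(CL/F). Hence Dose/AUC0-24 returns CL/F, and Dose/AUCinf returns (CL/F)/R. Example at 24 h: e^(−24k) = 0.5, R = 1/0.5 = 2.00, share = 0.50.

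**Simulation of the actual dosing history.** One-compartment oral model with true CL/F = 1 and an assumed absorption rate of 1 per hour, integrated directly. Linear-up/log-down analysis on sampling times to 96 h agreed within 0.005.

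| Assumed t1/2 | R | Dose/AUCinf as share of true CL/F, closed form (1/R) | Same, simulated | Dose/AUC0-24 as share of true CL/F, simulated |
|---|---|---|---|---|
| 6 h | 1.07 | 0.94 | 0.93 | 1.00 |
| 12 h | 1.33 | 0.75 | 0.74 | 1.00 |
| 24 h | 2.00 | 0.50 | 0.49 | 1.00 |
| 36 h | 2.70 | 0.37 | 0.37 | 1.01 |
| 48 h | 3.41 | 0.29 | 0.30 | 1.03 |
| 72 h | 4.85 | 0.21 | 0.23 | 1.10 |

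At short half-lives the simulated share is slightly below 1/R, because absorption leaves a little more drug beyond 24 h. At 48 h and longer it is slightly above 1/R, because steady state is not fully reached by Day 15. Vz/F calculated as (Dose/AUCinf)/λz carries the same share.

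**The other reading: CL/F = Dose/AUC0-24.** There is then no accumulation bias, but two rules no longer fit:

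- The R²-adj ≥ 0.7 condition withholds CL/F in any subject with a poor terminal fit, although the formula does not use that fit.
- The 20% rule can remove CL/F if it is counted among the parameters derived from AUCinf. With sampling to 96 h the extrapolated share in a mono-exponential decline is 2^(−96/t1/2). This is 2^(−96/48) = 25% at 48 h, and it passes 20% once t1/2 exceeds 96/log2(5) = 96/2.32 ≈ 41 h.

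**The case against.** The strongest reply is that no formula is printed. The implied one rests on CL/F appearing in an illustrative list in section 8.5.1.1. Section 8.5.1.3 lets the predose value stand in for a missing 24 h CBP-307 concentration on Day 15, which makes sense only near steady state and suggests the authors may have had steady-state handling in mind. This stands: the bias is conditional on Dose/AUCinf being used. It does not rescue the text, because under the steady-state reading the λz condition on CL/F is itself wrong.

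Several stronger readings are tempting, and the documents do not support them:

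- **A reader might infer that clearance will be reported at half its true value.** That needs both the inferred formula and a 24 h half-life, and the SAP gives neither.
- **A reader might infer that Vz/F should not depend on λz.** It legitimately does. Only its AUC term is in question.
- **A reader might infer that Day 15 AUCinf is wrongly defined or that a dosing-interval exposure is missing.** The SAP nowhere calls AUCinf a one-dose exposure. AUC0-24 is already a named endpoint in section 3 and is already derived on Day 15. A label on AUCinf is a clarification.
- **A reader might infer that the QTc conclusions are at risk.** They are not. Sections 6.1 and 6.2 of the cardiodynamic SAP use concentrations and geometric mean Cmax.

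It also stands that CL/F and Vz/F are not named endpoints, that section 8.5.3 plans no inferential PK analysis, and that CL/F can be recalculated later from dose and Day 15 AUC0-24. Finally, Dose/AUC0-24 is not exact at long half-lives, as the 72 h row shows.

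**Conclusion.** The point holds in conditional form, at moderate severity. As written, sections 8.5.1.1 and 8.5.1.2 imply Dose/AUCinf for Day 15 CL/F and Dose/(λz × AUCinf) for Vz/F. If that is done, both are understated by the accumulation factor, from about 6 to 7% at a 6 h half-life to about 70% at 48 h. If a steady-state calculation is meant, the bias disappears, but the R²-adj condition, and possibly the extrapolation rule, would needlessly drop valid clearances. A stated rule therefore needs correcting on either reading.

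The size rests on assumed half-lives, a one-compartment model and linear kinetics. The direction follows from mass balance and does not depend on the half-life chosen. The effect is confined to two descriptive PK parameters and to how AUCinf is read; the primary concentration-QTc and assay-sensitivity analyses are untouched.

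**What to change.** - **Section 8.5.1:** print the formulas for Day 15, CLss/F = Dose/AUC0-24 and Vz/F = Dose/(λz × AUC0-24). Label Day 15 AUCinf as including drug accumulated from earlier doses.
- **Section 8.5.1.1:** take CL/F off the λz list. Keep the λz and R²-adj criterion for AUCinf, t1/2 and Vz/F.
- **Section 8.5.1.2:** state that the 20% extrapolation rule does not apply to CL/F.
- **Steady-state check:** compare Day 15 predose and 24 h concentrations, and read the result together with the estimated half-life. Dose/AUC0-24 assumes near steady state and would be about 3% high at a 48 h half-life and 10% high at 72 h.

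The cost is a few lines of SAP text and a steady-state setting with a 24 h interval in the noncompartmental run. No new data are needed, since Day 15 AUC0-24 and the predose and 24 h samples are already planned.

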8.5.1.1. Criteria for the Calculation of Apparent Terminal Elimination Rate Constant and Half-life

The start of the terminal elimination phase for each subject will be defined by visual inspection and generally will be the first point at which there is no systematic deviation from the log-linear decline in concentrations.

The apparent terminal elimination rate constant (λ_z) will only be calculated when a reliable estimate can be obtained using at least 3 data points, preferably not including C_{max}, and the adjusted coefficient for determination of exponential fit (R²-adj) of the regression line is ≥ 0.7 . Parameters requiring λ_z for their calculation (eg, AUC_{inf}, t_{1/2}, CL/F, and V_z/F for Profile Day 15) will only be calculated if the R²-adj value of the regression line is ≥ 0.7 .

The following regression-related diagnostic PK parameters will be determined, when possible:

Parameter	Units	Definition
λ_z	1/h	apparent terminal elimination rate constant
λ_z Upper	h	end of exponential fit
λ_z Lower	h	start of exponential fit
λ_z N	NA	number of data points included in the log-linear regression
λ_z Span Ratio	NA	time period over which λ_z was determined as a ratio of $t_{1/2}$
R ² -adj	NA	adjusted coefficient for determination of exponential fit

Where possible, the span of time used in the determination of λ_z (ie, the difference between λ_z Upper and λ_z Lower) should be ≥ 2 half-lives. If the λ_z Span Ratio is < 2 , the robustness of the $t_{1/2}$ values will be discussed in the clinical study report (CSR).

8.5.1.2. Criteria for Calculation and Reporting of Area Under the Concentration-time Curve

The minimum requirement for the calculation of AUC will be the inclusion of at least 3 consecutive concentrations above the lower limit of quantification. If there are only 3 consecutive concentrations, at least 1 should follow C_{max} .

If the extrapolated area is $>20\%$, AUC_{inf} (and derived parameters) may be excluded from the summary statistics at the discretion of the sponsor or pharmacokineticist.

8.5.1.3. Criteria for Handling Concentration Below the Limit of Quantification or Missing Concentrations for Pharmacokinetic Analys

Plasma concentrations below the limit of quantification (BLQ) will be assigned a value of 0 before the first measurable concentration and thereafter BLQ concentrations will be treated as missing. The following rules apply to the specific situations defined below:

- If an entire concentration-time profile is BLQ, it will be excluded from PK analysis.
- Where 2 or more consecutive concentrations are BLQ at the end of a profile, the profile will be deemed to have terminated and any further quantifiable concentrations will be set to missing for the calculation of the PK parameters, unless they are considered to be a true characteristic of the profile of the drug.
- If a predose plasma concentration is missing, it will be set to 0 by default within Phoenix WinNonlin for the first dosing day (Study Profile Day 1).
- For multiple dose part of the study (Study Profile Day 15), if the CBP-307 concentration at 24 hours postdose is missing, this may be substituted with the predose.

8.5.1.4. Treatment of Outliers in Pharmacokinetic Analysis

If a value is considered to be anomalous due to being inconsistent with the expected PK profile, it may be appropriate to exclude the value from the PK analysis. However, the exclusion of any data must have strong justification and will be documented in the CSR.

Any quantifiable predose concentration value on the first dosing day (Study Profile Day 1) will be considered anomalous and set to missing for the PK analysis. This will be set to 0 by default in Phoenix WinNonlin.

8.5.2. Presentation of Pharmacokinetic Data

All PK concentrations and parameters will be listed.

Summary tables, arithmetic mean (+ standard deviation [SD]) figures, overlaying individual figures, and individual figures by appropriate treatment and time postdose will be provided for plasma PK concentrations. All figures will be produced on both linear-linear and linear-logarithmic scales, with the exception of figures across all days, which will be produced on the linear-linear scale only. The +SD bars will only be displayed on the linear-linear scale.

Summary tables by appropriate treatment will be provided for all PK parameters, with the exception of diagnostic regression-related PK parameters.

A subject may be excluded from the PK summary statistics and statistical analysis if the subject has an AE of vomiting that occurs at or before 2 times the median t_{max} . Where subjects tested positive for COVID-19, data will only be listed where available.

If the actual time of sample collection deviates from the allowed PK sample collection window, the plasma concentration will be flagged and excluded from the summary statistics.

Individual concentrations deemed to be anomalous will be flagged in the listings and excluded from the summary statistics.

For plasma concentration data the following rules will apply:

- Values that are BLQ will be set to 0 for the calculation of summary statistics.
- Arithmetic mean or median values that are BLQ will be presented as 0.

For PK parameters the following rule will apply:

Geometric mean and coefficient of variation will not be calculated for t_{last} and t_{max}

8.5.3. Pharmacokinetic Statistical Methodology

No inferential statistical analyses are planned.

8.6. Safety and Tolerability Assessments

8.6.1. Adverse Events

All AEs will be coded using the Medical Dictionary for Regulatory Activities (MedDRA) Version 24.0 (or higher if a new version is issued during the study; see the DMP for more details).

A treatment-emergent adverse event (TEAE) will be defined as an AE that starts during or after dosing on Day 1, or starts prior to dosing on Day 1 and increases in severity after each dosing.

A treatment related TEAE will be defined as a TEAE with a relationship of possibly related or related to the study treatment, as determined by the investigator.

All AEs will be listed. In addition to the data recorded in the database, the listings will include derived onset time and duration. Onset time will be calculated from the time of dosing for TEAEs only. Where the last associated dose is referring to the last dose received prior to the start of a TEAE.

The frequency of subjects with TEAEs and the number of TEAEs will be summarized for the following categories:

- TEAEs (overall, serious, leading to discontinuation, and leading to death) by treatment
- TEAEs by severity and treatment
- Treatment-related TEAEs (overall, serious, leading to discontinuation, and leading to death) by treatment
- Treatment-related TEAEs by severity and treatment

The frequency of subjects will be summarized separately for TEAEs and treatment-related TEAEs by the following:

- System organ class, preferred term, and treatment
- Preferred term and treatment

For the AE data the following rules will apply:

- For the derivation of treatment-emergent status (applicable to all AEs): The collecting time window for AEs will be from after the time of signing the ICF until end of study (EOS)
- For the derivation of treatment-emergent status (applicable to all AEs): If the start date/time of an AE is incomplete or missing, an AE will be assumed to be a TEAE, unless the incomplete start date/time or the end date/time indicates an AE started

before dosing. For the derivation of treatment-related status (applicable to TEAEs only): If the study treatment relationship for a TEAE is missing, a TEAE will be assumed to be a treatment-related TEAE.

- For the derivation of onset time (applicable to TEAEs only): If the start date/time of a TEAE is missing, onset time will not be calculated. If the start date/time of a TEAE is incomplete, where possible, the minimum possible onset time will be calculated and presented in ‘ \geq DD:HH:MM’ format (eg, if the date/time of dosing is 01MAY2019/08:00 and recorded start date/time of a TEAE is 03MAY2019, then the minimum possible onset time will be calculated by assuming a TEAE started at the first hour and minute of 03MAY2019 [03MAY2019/00:00], thus will be presented as onset time \geq 01:16:00 in the listing). If the start date of a TEAE is the same as the date of dosing but the start time of a TEAE is missing, an onset time will be presented as ‘ \geq 00:00:01’. Any clock changes will be accounted for in the derivation.
- For the derivation of duration (applicable to all AEs): If the end date/time of an AE is missing, duration will not be calculated. If the start or end date/time of an AE is incomplete, where possible, the maximum possible duration will be calculated and presented in ‘ \leq DD:HH:MM’ format (eg, if the start of an AE date/time is 01MAY2019/08:00 and its recorded end date/time is 03MAY2019, then the maximum possible duration will be calculated by assuming an AE ended at the last hour and minute of 03MAY2019 [03MAY2019/23:59], thus will be presented as duration \leq 02:15:59 in the listing). Any clock changes will be accounted for in the derivation.
- For the calculation of TEAE summary statistics: If the severity of a TEAE is missing, that TEAE will be counted under the ‘missing’ category.
- For the calculation of TEAE summary statistics: Counting rules for TEAEs: The collecting time window for TEAEs will be from the time of dosing on Day 1 until study completion (Day 1~EOS).
 - For CBP-307 0.05mg dose, only count/collect/record TEAEs that starts or increases in severity during the dosing level of CBP-307 0.05mg (from the time of dosing 0.05mg on Day 1 until the start of dosing 0.1mg on Day 2), irrespective of the TEAE’s ending time.
 - For CBP-307 0.1mg dose, only count/collect/record TEAEs that starts or increases in severity during the dosing level of CBP-307 0.1mg (from the time of dosing 0.1mg on Day 2 until the start of dosing 0.2mg on Day 3), irrespective of the TEAE’s ending time.
 - For CBP-307 0.2mg dose, only count/collect/record TEAEs that starts or increases in severity during the dosing level of CBP-307 0.2mg (from the time of dosing 0.2mg on Day 3 until the start of dosing 0.5mg on Day 7), irrespective of the TEAE’s ending time.

- For CBP-307 0.5mg dose, only count/collect/record TEAEs that starts or increases in severity from the time of dosing 0.5mg on Day 7 until study completion (Day 7~EOS), irrespective of the TEAE's ending time.
- For the calculation of TEAE summary statistics: If a subject experienced multiple TEAEs with the same preferred term for the same treatment, this will be counted as 1 TEAE for that treatment under the maximum severity recorded.

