Days 7 to 15	Group 1 Group 2A Group 2B	5 × 0.1 mg			
Day 16	Group 1 Group 2A Group 2B		1 capsule 1 capsule 1 capsule	1 × 400 mg	1 tablet 1 tablet

A schematic of the study design is presented in

[Figure 1.](#)

Figure 1: Study Design

Potential subjects will be screened to assess their eligibility to enter the study within 27 days prior to the first dose administration. Subjects will be admitted into the study site on Day -2 (or on Day -4 depending on the clinical site's requirement for Coronavirus Disease 2019 [COVID-19] testing) and will remain at the study site until discharge on Day 19. Treatment administration will occur on Days 1, 2, 3 to 6, 7 to 15, and 16 under fasting conditions (all subjects will receive placebo on Day -1). Continuous cardiodynamic ECG monitoring and recording will begin at least 25 hours prior to the administration of study treatments on Day 1 and continue through 24 hours after the administration of study treatments on Days 1, 6, 15, and 16 and at corresponding timepoints on the day before dosing, ie, Day -1. Blood samples for PK analysis will be collected predose and at each postdose cardiodynamic ECG timepoint. Additional PK samples will be collected at 72 and 96 hours following dosing on Day 15. Subjects will return to the study site for a follow-up visit on Day 29±2 days.

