6. STUDY TREATMENTS

The study treatment names and ordering to be used in the TFLs are presented in [Table 1](#).

Table 1: Presentation of Study Treatments in TFLs

Study Treatment	Order in TFLs
Placebo	1
400 mg Moxifloxacin	2
0.05 mg CBP-307	3
0.1 mg CBP-307	4
0.2 mg CBP-307	5
0.5 mg CBP-307	6

All TFLs will be based on actual treatments (eg, if subject was assigned to receive placebo but was wrongfully dosed with active treatment they would be summarized and listed under active treatment).

The study treatment sequence names, abbreviations, and ordering to be used in the TFLs are presented in [Table 2](#).

Table 2: Presentation of Study Treatment Sequences in TFLs

Study Treatment Sequence	Abbreviation	Order in TFLs
1 capsule of CBP-307 matched placebo on Day -1 -> 1 × 0.05 mg CBP-307 and 1 tablet of Moxifloxacin matched placebo on Day 1 -> 1 × 0.1 mg CBP-307 on Day 2 -> 2 × 0.1 mg CBP-307 on Days 3 to 6 -> 5 × 0.1 mg CBP-307 on Days 7 to 15 -> 1 capsule of CBP-307 matched placebo and 1 tablet of Moxifloxacin matched placebo on Day 16	Group 1	1
1 capsule of CBP-307 matched placebo on Day -1 -> 1 capsule of CBP-307 matched Placebo and 1 × 400 mg Moxifloxacin tablet on Day 1 -> 1 capsule of CBP-307 matched Placebo on Day 2 -> 2 capsules of CBP-307 matched Placebo Days 3 to 6 -> 5 capsules of CBP-307 matched Placebo on Days 7 to 15 -> 1 capsule of CBP-307 matched placebo and 1 tablet of Moxifloxacin matched placebo on Day 16	Group 2A	2
1 capsule of CBP-307 matched placebo on Day -1 -> 1 capsule of CBP-307 matched Placebo and 1 tablet of Moxifloxacin matched placebo on Day 1 -> 1 capsule of CBP-307 matched Placebo on Day 2 -> 2 capsules of CBP-307 matched Placebo Days 3 to 6 -> 5 capsules of CBP-307 matched Placebo on Days 7 to 15 -> 1 capsule of CBP-307 matched placebo and 1 × 400 mg Moxifloxacin tablet on Day 16	Group 2B	3

The summaries will be based on planned treatment sequences and listings will be based on actual treatment and sequences.

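### The worsening limb of the TEAE definition (main SAP 8.6.1) asks for an increase in severity after each dose, which is practically unattainable over 16 daily doses and conflicts with the SAP's own counting rules

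*SAP*

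**What the plan says.** Main SAP section 8.6.1 defines a TEAE by two limbs. The onset limb takes "an AE that starts during or after dosing on Day 1". The worsening limb takes an event that "or starts prior to dosing on Day 1 and increases in severity after each dosing".

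Further down, section 8.6.1 gives counting rules for the four CBP-307 dose levels. For the lowest level the instruction is to "only count/collect/record TEAEs that starts or increases in severity during the dosing level of CBP-307 0.05mg", and the same pattern is repeated for 0.1, 0.2 and 0.5 mg. No such rule is given for placebo or moxifloxacin.

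Section 4 fixes which events can begin before Day 1. Between consent and the start of study treatment, "only SAEs will be reported". From then on the net is wider: "After placebo administration to all subjects on Day -1, all AEs, whether volunteered, elicited, or noted upon physical examination, will be recorded". Section 4 also gives the dosing schedule: "Treatment administration will occur on Days 1, 2, 3 to 6, 7 to 15, and 16 under fasting conditions".

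**The concern.** The worsening limb is the only way for an event with onset before Day 1 dosing to become treatment-emergent. The rule for incomplete dates adds to its importance: an event whose partial date shows a start before dosing is not assumed to be a TEAE, so it too depends on this limb.

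Every AE summary in section 8.6.1 is built on TEAEs: overall, serious, leading to discontinuation or death, by severity, treatment-related, and by system organ class and preferred term. Incidence and severity of AEs is a stated safety endpoint (section 3). A limb that practically no completer can satisfy would remove worsening of such events from all these tables. For example, a mild headache that began on Day -1 and became severe after the step to 0.5 mg on Day 7 has worsened after one dose, not after each. On a literal reading it is not a TEAE.

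**Working it through.** The plan states no figure on this point, so there is none to reproduce. The check is a count and a comparison of rules.

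**Number of doses (section 4).** Day 1, Day 2, Days 3 to 6, Days 7 to 15 and Day 16 give 1 + 1 + 4 + 9 + 1 = 16 dosing days from Day 1. In Group 1 the last is placebo (section 6, Table 2: "5 × 0.1 mg CBP-307 on Days 7 to 15 -> 1 capsule of CBP-307 matched placebo"), so 15 are CBP-307 days. The Day -1 placebo is additional.

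**Increases a severity scale allows.** With *k* ordered grades, an event that starts at the lowest grade and never eases can increase at most *k* − 1 times. An increase after each of *d* doses therefore needs *k* ≥ *d* + 1.
- For a completer, *d* = 16, so *k* ≥ 17.
- The SAP does not give the number of grades. Assuming 3 to 5, the maximum is 2 to 4 successive increases.
- Under that assumption the literal limb can be met only by a subject who stops after at most 2 to 4 doses from Day 1.

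**Definition against counting rules (both in section 8.6.1).**

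| | Definition, worsening limb | Counting rules |
|---|---|---|
| Increases needed | one after each dose | one within the dose-level window |
| Applies to | any AE with onset before Day 1 dosing | events already called TEAEs |
| Treatments covered | all | CBP-307 0.05, 0.1, 0.2 and 0.5 mg only |

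The 0.05 mg window opens at Day 1 dosing and closes when 0.1 mg is given on Day 2. An event that starts inside that window is already counted by its start. The words about increasing severity therefore add something at this level only for events that began before Day 1 dosing, and for those one increase is enough. This is good evidence of intent, although the same phrase is repeated at every level and may be template wording.

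**Which events are exposed.** Under section 4 these are AEs that start between the Day -1 placebo and Day 1 dosing, plus SAEs from consent onward. Section 8.6.1 itself opens the AE window at consent, which would be wider; the narrower section 4 scope is used here. Subjects are admitted on Day -2 (Day -4 at some sites), but it is the recording rule, not admission, that sets the window.

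**Weight of one event.** One Group 1 subject is 1/34 = 2.9 percentage points (1/32 = 3.1 on the group size in main SAP section 5). This is the weight of a single subject, not an estimate of how many events would be lost.

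**The case against.** A reader might infer that an event beginning before Day 1 and worsening on CBP-307 can never be treatment-emergent in this trial. The documents do not support that, for four reasons.

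- *Each dosing* can be read as *a given dosing*, and the 0.05 mg counting rule points that way. The text is ambiguous and internally inconsistent; it does not clearly exclude these events.
- Even on the literal reading, a subject who stops after one or a few doses can meet the limb.
- The ceiling of 2 to 4 increases assumes that severity does not fall between doses. An event that eases overnight and worsens after each daily dose could increase repeatedly on a short scale, if it is kept as one record.
- If a worsening is entered as a new AE record, the new record qualifies by onset. The SAP does not say how worsening is recorded, and that is commonly set in the protocol or eCRF instructions, which are not at hand.

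The consequence is also limited. The pre-dose window is about a day for non-serious events, all AEs are listed in any case, and no inferential safety analysis is planned (section 8.6.7).

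All of this stands, and it lowers the severity. It does not justify keeping the wording. The counting rules operate only on events that have already passed the definition, so they cannot admit one that failed it. They also give no support to the lenient reading for placebo and moxifloxacin, so a programmer could apply different standards in Group 1 and in Groups 2A and 2B. Section 1 says that the SAP supersedes the protocol's statistical considerations, so protocol wording is not a safe fallback.

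**Conclusion.** The point holds as a defect in a derivation rule. Read literally, the worsening limb is practically unattainable for anyone dosed beyond the first few days, and it conflicts with the single-increase counting rules in the same section. Those rules show the probable intent but do not formally repair the definition for any arm.

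The effect arises only if three conditions hold together: the sentence is programmed literally, the event began before Day 1 dosing and later worsened, and the worsening stays on the original record. Such an event would then be absent from all TEAE tables and visible only in listings. The number of such events cannot be derived from the documents and is probably small. AEs starting during or after Day 1 dosing are untouched, and so is the QTc analysis. Severity is minor to moderate.

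The arithmetic rests on an assumed scale of 3 to 5 grades and on severity not easing between doses.

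**What to change.** In section 8.6.1, replace *after each dosing* with *after any dose on or after Day 1*. One increase is then enough, which is attainable on any scale with at least two grades and agrees with the counting rules.

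Add that, for all treatments including placebo and moxifloxacin, such an event is counted under the treatment during which it worsened, at the increased severity. For the CBP-307 dose levels this confirms the attribution already written. For placebo and moxifloxacin it fills a gap.

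The cost is one changed phrase and one added sentence. No new data are needed, and the change should be made before the TEAE flag is programmed.
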